any frame with FD > 0.5 mm from the regression analysis described below, yielding a scrub ratio for each subject. As it has been demonstrated that as many as 60% of frames can be removed and still yield analyzable results,(88, 89) we will use 60% deleted frames as a cutoff for analyzable subjects. Three-compartment segmentation of the high-resolution structural image from the VBM8 normalization will be applied to the functional time series to extract cerebral spinal volume (CSF) and white matter (WM) compartments, which will be subjected to a principal component analysis to identify the top 5 components in each,(90) which corresponds to heart rate and respiratory effects on the blood oxygenation level-dependent signal.(91) Adjusted time courses will be derived from sequential regressions of the time series with the following: Linear trend, 6 motion parameters, their temporal derivatives, the quadratics of these 12 parameters, 5 components from the PCA of CSF, 5 components of PCA of WM, followed by band pass filtering from 0.01 – 0.1 Hz, and then motion scrubbing. ICA-AROMA will be used to de-noise the data and remove additional, residual motion artifacts.(92) Global signal regression (GSR) will not be done because of concerns about non-uniform transformation of correlations introduced by GSR, problematic for group comparisons.(93) For the primary analysis, the time-course from a 6 mm radius sphere at the site of stimulation will be entered into the multiple regression and correlated with every other gray-matter voxel time-course in the brain for each subject. Correlation coefficients are Z-transformed and then entered into the second level, between-subject analyses as two-sided, paired t-tests to compare between sessions. Statistical inference will be controlled as above.

(H1.2) iTBS to dlPFC, compared to vertex stimulation, will increase FPN connectivity during resting state BOLD. Because TMS effects are observed away from the site of stimulation,(38-41) we are testing functionally-defined FPN networks. We recognize that the FPN defined by n-back will not be identical to the FPN defined by a dlPFC seed-based connectivity, although the two significantly overlap.

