Exploratory analysis, global brain connectivity: We will examine a graph-theoretic measure known as global brain connectivity (GBC).(94) GBC reflects the strength of local connectivity, similar to degree connectivity, except that no arbitrary thresholding of connections ('edges') is required; rather, the value of the connection strength (r-to-Z transformed) is summed. GBC in the dlPFC has been shown to decrease with electro-convulsive therapy, with the degree of change related to symptom improvement;(95) thus, we will test to see if iTBS to the dlPFC has an effect on GBC in the dlPFC. Two types of analyses will be conducted. In the first, we will average the connectivity for the 6 mm radius sphere at the site of stimulation and compare that for dlPFC stimulation and vertex stimulation. Alpha level will be $p < 0.05$, two-sided. In the second analysis, we will search for network effects. Time courses will be extracted from 10 mm diameter spheres based on a set of 264 nodes distributed throughout the brain,(96) generating a cross-correlation matrix of Pearson r-values. Z-transformed r-values (connectivity strengths) for each of the 264 nodes with every other node (global brain connectivity) are summed, and connectivity strengths with the nodes within 13 specified networks are also summed. Connectivity measures (13 per subject) will then be entered into second level repeated measures ANCOVA, with gender as between factor, network and session (dlPFC, vertex) as within-factors, and meanFD and age as co-variates, testing the hypothesis of change in GBC by network. We will also test exploratory effects across all 13 networks (with alpha level set to $0.05/13=0.0038$), and we will test for effects on GBC (connectivity between all nodes).

Primary outcome measure #3, rCBF at stimulation target

Analysis plan: The *pCASL* images will be realigned using SPM12 realignment routines and denoised using compCor(90) and then used to calculate the perfusion rate at each voxel using a

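### Exploratory GBC network analysis: summed, unscaled network scores let an equal per-connection shift register as a network-by-session effect and let large networks mask small ones

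*Combined protocol and SAP*

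**What the plan says.** The relevant text is in Section 8.0, Specific Aim 1, under the exploratory analysis of global brain connectivity.

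- GBC is defined as a total: "the value of the connection strength (r-to-Z transformed) is summed".
- The network search uses "a set of 264 nodes distributed throughout the brain". Besides the total for each node with all others, "connectivity strengths with the nodes within 13 specified networks are also summed".
- The model is stated as follows: "Connectivity measures (13 per subject) will then be entered into second level repeated measures ANCOVA". Gender is the between-subject factor, with "network and session (dlPFC, vertex) as within-factors, and meanFD and age as co-variates". Its purpose is "testing the hypothesis of change in GBC by network".
- Session effects are also tested across the 13 networks at 0.05/13, and on connectivity between all nodes.

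Averaging is stated only for the separate analysis of the 6 mm sphere at the stimulation site. For the 13 network scores the plan gives no division by node or connection count, no standardisation, no node count per network and no sphericity correction.

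**The concern.** A sum of connection strengths grows with the number of connections in it. When such sums are compared across networks in one model, the network-by-session term mixes two questions: whether networks responded differently, and whether they differ in size. Two errors can follow.

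1. A dlPFC-minus-vertex change that is equal for every connection moves a large network's score more than a small one's, and so appears as an interaction.
2. The variance in the term comes mainly from the largest networks, so a real change confined to a small network is hard to see. This needs no uniform shift.

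This term is the overall test of network specificity in a search meant to help localise iTBS effects under Aim 1. A positive result would be read as certain networks responding to stimulation and others not.

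**Working it through.** **Inputs from the documents.** 264 nodes, 13 networks, two sessions in the model, unscaled sums (Section 8.0); 40 analysable subjects (Section 4.1). Network sizes, shift and noise are not given and are assumed below.

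**The plan's own figure.** 0.05/13 = 0.003846, which rounds to the stated 0.0038.

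**Algebra.** Let network k's score be the sum of m_k connections. If every connection changes by d between sessions, the score changes by d × m_k. The interaction contrast between networks j and k is d × (m_j − m_k), which is zero only if d = 0 or the counts are equal. If all 264 nodes are assigned, equal node counts are impossible, since 264/13 = 20.31.

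**Scale.** The wording allows two readings of what is summed. Take assumed networks of 40 and 10 nodes:

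- Connections within the network, n(n−1)/2: 780 and 45, ratio 17.3. A shift of 0.02 moves the sums by 15.6 and 0.9.
- Connections of the network's nodes to all other nodes, n × 263: 10,520 and 2,630, ratio 4.

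**Simulation A.** Assumed: 40 subjects; sizes 6, 8, 10, 12, 14, 16, 18, 20, 24, 28, 32, 36, 40 (total 264); between-subject SD of the uniform shift 0.03; network-specific SD 0.04; Greenhouse-Geisser test at 0.05; 2,000 runs per cell. Rejection of the network-by-session term when every connection shifts equally:

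| Mean shift in Z | Mean per connection | Sum, proportional to nodes | Sum, proportional to edges |
|---|---|---|---|
| 0 | 0.03 | 0.05 | 0.04 |
| 0.01 | 0.03 | 0.19 | 0.28 |
| 0.02 | 0.03 | 0.67 | 0.82 |

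Repeat runs at a shift of 0.02 gave 68% (nodes) and 81% (edges) on sums, and 2% to 4% on means.

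**Simulation B, varying the sizes.** Assumed: subject-wide SD 0.08, network noise SD 0.06, 1,000 runs per cell; gender, age and motion omitted. Greenhouse-Geisser rejection on sums, within-network reading:

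| Network sizes | Shift 0.03 | Shift 0.05 |
|---|---|---|
| All 20 (260 nodes) | 0.03 | 0.02 |
| 20–21 | 0.05 | 0.05 |
| 14–30 | 0.42 | 0.83 |
| 8–34 | 0.52 | 0.92 |
| 5–58 | 0.47 | 0.90 |

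On the node-to-all reading at 0.05, the last three rows become 0.51, 0.84 and 0.92. A multivariate test (Hotelling T²) on those three size sets at 0.05 rejected in 0.24 to 0.55 of runs, so it reduces the problem without removing it. On means, Greenhouse-Geisser rejection was 0.02 to 0.05 in every cell.

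**No mean shift.** Unequal scales break sphericity. In the three unequal size sets of simulation B, the uncorrected F on sums rejected in 0.06 to 0.19 of runs; with Greenhouse-Geisser the range was 0.03 to 0.06.

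**Masking.** With a true change of +0.03 confined to a 10-node network, under simulation A's assumptions, the interaction was significant in 82% to 83% of runs on means and 4% to 9% on sums.

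**What scaling does not touch.** Multiplying one network's scores by a constant leaves its paired session test unchanged: p = 0.0682 for a simulated score and for the same score × 190. The 13 single-network tests and the all-node GBC test therefore stand.

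**The case against.** The strongest reply is that the plan already guards against the obvious sources of a uniform shift and already contains a check for one.

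- *Design.* The three stimulation sessions are counterbalanced. They are scheduled at the same time of day where possible, and sleep and substance use are recorded. The resting-state pipeline removes CSF and white-matter components tied to heart rate and respiration, and adds ICA-AROMA.
- *Check.* Under simulation A's assumptions, a test of the global change rejected in 97% of runs at a shift of 0.02 and 50% at 0.01. That is more often than the interaction does on sums.
- *Estimand.* The plan defines GBC as a sum, and choosing a sum or a mean is partly a choice of what to estimate.

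Much of this stands. A reader might infer that ordinary variation between days in arousal or breathing, left in because "Global signal regression (GSR) will not be done", would itself produce false network effects. The documents do not support that. Under counterbalancing, such variation averages to zero between conditions. Raising the subject-wide SD from 0.03 to 0.08 with no mean shift left rejection at 0.047 (nodes) and 0.050 (edges) under Greenhouse-Geisser. A mean difference tied to condition is needed: a real brain-wide effect of dlPFC stimulation, or a state difference linked to the stimulation site.

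A reader might also infer that a uniform shift is bound to be significant, or that the plan cannot tell global from network-specific change. Neither follows. Significance depends on quantities that the documents do not give, and the all-node test is informative.

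What the reply does not remove is that the interaction, as scaled, does not answer the question put to it, and that small-network effects are masked even with no uniform shift.

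**Conclusion.** The point holds as a minor one. As written, the network-by-session term confounds network specificity with network size unless the networks contribute equal numbers of connections. That much is algebra. Its practical size rests on assumed network sizes, shifts and noise. With sizes of 6 to 40 nodes, rejection under an equal per-connection change is 19% to 28% at a shift of 0.01 and 67% to 82% at 0.02, against about 3% on means. With sizes of 20 to 21 nodes there is essentially no excess. The risk is that a global condition effect is labelled network-specific, or that an effect in a small network is missed. It is not that an effect is created from balanced nuisance variation, provided a sphericity correction is used. The analysis is exploratory, and no outcome listed as primary or secondary in Section 2.0 depends on it.

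**What to change.** In the exploratory GBC paragraph of Section 8.0:

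1. Define each network score as the mean Z per summed connection, that is, the sum divided by the number of connections in it. State which connections are counted and how many nodes each network has.
2. Test network by session on these means with a named sphericity correction, such as Greenhouse-Geisser.
3. State that the interaction will be interpreted alongside the all-node GBC test.

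The cost is a sentence or two in the plan and a division in the script. No new data are needed, and the single-network p-values do not change.

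There is a small downside. Means give small networks the same weight as large ones although their means are noisier. Means also take an equal additive change in Z as the null. If a global change were proportional to baseline connectivity (assumed baseline mean Z 0.15 to 0.45), the interaction on means still rejected in 46% of runs at an average shift of 0.02 and 11% at 0.01. That is a further reason to read it beside the all-node test.

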2.0 Study aims and outcome measures

Specific Aim 1: Localize neural effects of dlPFC TBS We will show that persisting neural changes induced by TBS to the dlPFC will affect the FPN. We predict that TBS alone (subjects not performing a cognitive task), compared to vertex stimulation, will increase fMRI activation in the FPN during the n-back and increase FPN connectivity during resting state BOLD. We also predict that TBS will increase resting perfusion in the FPN. Exploratory analyses will search for regions outside the FPN that change with stimulation to develop a comprehensive picture of how TBS to the dlPFC interacts with brain networks.

Specific Aim 2: Demonstrate modulation of the effect of dlPFC TBS by a cognitive task We predict that FPN changes during iTBS administered while subjects perform the n-back task will be greater than when they are not performing a task. We will also test the same hypothesis for BOLD resting state connectivity, and ASL-measured perfusion, in addition to exploratory hypotheses on brain networks outside the FPN.

Primary outcome measures for Aims 1 & 2:

- 1) 2-back minus 1-back BOLD activation, voxelwise in FPN
- 2) FPN connectivity to dlPFC TBS stimulation target
- 3) rCBF at stimulation target

Secondary outcome measures for Aims 1 & 2:

- 1) 2-back minus 1-back BOLD activation, voxelwise in whole brain
- 2) rCBF in FPN

Specific Aim 3: Demonstrate improvement in cognitive control with TBS, modulated by cognitive task during stimulation We will test predictions that n-back performance will improve following TBS to dlPFC, but not vertex, and will improve even more following TBS during n-back performance. Exploratory analyses will examine correlations between performance changes and network changes, suggesting mechanistic connections between TBS and performance changes.

Primary outcome measure for Aim 3: accuracy to 2-back

[figure not shown]
Secondary outcome measures for Aim 3: d-prime, reaction time

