8.0 Statistical analysis

Analyses described below represent planned analyses for primary and secondary measures. However, actual implementation of these analyses may differ slightly from what is described below, although the primary and secondary outcome measures will be as described.

Specific Aim 1: Localize neural effects of dIPFC iTBS

Primary outcome measures:

Primary outcome #1, BOLD activation: 2-back minus 1-back BOLD activation, voxelwise in FPN

Analysis Plan: MRI data analysis and strict quality control will use validated and established routines implemented in our laboratory. For processing BOLD images, we will use well-tested routines from FSL 5.0.1 and SPM12 for slice timing and realignment algorithms and spatial normalization (MNI-152) procedures implemented in VBM8. First-level analysis will use the general framework of the modified General Linear Model,(82) implemented in SPM12 with temporal convolution. For the *n-back* data the first-level design matrix will include regressors for 2-back and 1-back, iTBS/MRI session and 12 realignment parameters (including temporal derivatives of 6 realignment parameters). Second-level, between-subject analysis will consist of two-sided, one-sample t-tests for primary effects. For statistical inference across the FPN, and the entire brain, we will use topological false discovery rate (FDR)(83) providing corrected probabilities at $p<0.017$ ($0.05/3$, accounting for testing of 3 primary MRI measures). Given *a priori* hypotheses about FPN, a mask of activation (2-back minus 1-back, $p<0.001_{\text{uncorr}}$) at the group level, using all 4 MRI runs to provide the most representative mask, will be used as small volume correction.

(H1.1): iTBS to dlPFC, compared to vertex stimulation, will increase fMRI activation in the FPN during the n-back.

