two-compartment model, assuming gray matter T1 of 1400 ms. and 90% labeling efficiency. ROI analysis of the CBF images will occur in native space, using the FPN mask derived from n-back activation, warped to individual anatomy. A two-sided, paired t-test will test for effect of sessions, with $p < 0.017$ as alpha. Secondary analyses will be performed on 6 cm radius sphere at the site of stimulation, in addition to a whole brain, voxel-wise search for changes in gray-matter tissue, using topological FDR to correct for multiple comparisons to $p < 0.017_{\text{corr}}$.

(H1.3) iTBS to dlPFC, compared to vertex stimulation, will increase resting perfusion at the site of stimulation. PET studies of high frequency TMS have reported increased CBF at the dlPFC,(97) a finding which motivates our hypothesis here. However, a cTBS study by our co-investigator ([name]) also found *increased* CBF after supposedly inhibitory stimulation of dlPFC,(98) so we will be performing a two-tailed t-test here. While the primary analysis will focus on the site of stimulation, a secondary analysis will focus on the FPN network, defined by the n-back task.

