To examine state-dependency and modulation of iTBS effects by task, we will contrast MRI measures following iTBS applied to the dlPFC while subjects perform the n-back with MRI measures following iTBS compared to when they are in an unconstrained, resting state. The general analysis plan will use the same work-up of the imaging data as described above, the only difference being the MRI sessions that are compared with each other. Although directions of change are difficult to predict, we are predicting increasing activity as has been reported for iTBS applied during a deep encoding memory paradigm and not observed during shallow-encoding.(106) However, it is possible that cortex may become more efficient and less activation may be seen. The following primary hypotheses will be tested:

Primary outcome #1, BOLD activation: 2-back minus 1-back BOLD activation, voxelwise in FPN
(H2.1) For dlPFC stimulation during performance of a n-back task, compared to dlPFC
stimulation in a resting, unconstrained mental state, FPN activation to the n-back task will be
greater. For this analysis, the region of interest will be the FPN taken from the activation mask,
as described above. For a secondary measure to test H2.1, we will examine whole brain
activation, since change may occur outside this region of interest.

Primary outcome measure #2, BOLD connectivity: FPN connectivity to dlPFC iTBS stimulation
target

(H2.2) For dlPFC stimulation during performance of a n-back task, compared to dlPFC
stimulation in a resting, unconstrained mental state, connectivity with the dlPFC site of
stimulation will increase. For this analysis, the region of primary interest will be connectivity to
site of stimulation.

Primary outcome measure #3, rCBF at stimulation target

(H2.3) For dlPFC stimulation during performance of a n-back task, compared to dlPFC
stimulation in a resting, unconstrained mental state, resting perfusion at stimulation site will
increase. The primary region of interest will be the site of stimulation, and secondary analyses
will focus on the FPN, defined by n-back activation.

Specific Aim 3: Demonstrate improvement in cognitive control with iTBS, modulated by cognitive task during stimulation

Primary outcome measure: accuracy to 2-back

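### The rCBF analysis paragraph reverses the declared primary and secondary regions, and the only size it gives for the primary region is a sphere of 6 cm radius

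*Combined protocol and SAP*

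**What the plan says.** Most of the document points one way. The outcome list in section 2.0 gives "rCBF at stimulation target" as the third primary measure for Aims 1 and 2, and puts FPN perfusion among the secondary measures. The section 8.0 heading agrees: "Primary outcome measure #3, rCBF at stimulation target". So does H1.3: "While the primary analysis will focus on the site of stimulation, a secondary analysis will focus on the FPN network". H2.3 says the same for Aim 2: "The primary region of interest will be the site of stimulation". The opening of section 8.0 allows small departures in implementation, "although the primary and secondary outcome measures will be as described".

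The analysis paragraph under that primary heading points the other way. It begins: "ROI analysis of the CBF images will occur in native space, using the FPN mask derived from n-back activation". The next sentence supplies the two-sided paired t-test and the 0.017 threshold. The stimulation site then appears under a different label: "Secondary analyses will be performed on 6 cm radius sphere at the site of stimulation". That sentence goes on to a whole-brain voxelwise search at an FDR-corrected 0.017.

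For Aim 2, section 8.0 states: "The general analysis plan will use the same work-up of the imaging data as described above". The sphere described for Aim 1 is therefore the one Aim 2 inherits.

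**The concern.** This is the only paragraph that brings the rCBF region, test and alpha together, so it is the one an analyst would implement. Followed literally, it tests the declared secondary region in the primary slot and relegates the declared primary region.

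An analyst who follows H1.3 and H2.3 instead meets a second problem. The only stated size for the target sphere is 12 cm across, far larger than a focal dlPFC site, so averaging over it would dilute any local change heavily.

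Two readings of one primary outcome also leave room to settle the region after the data have been seen. The 0.05/3 threshold assumes one test per primary MRI measure and would not hold in that case.

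**Working it through.** **The plan's own figure.** Section 8.0 divides 0.05 by three primary MRI measures: 0.05/3 = 0.01667, which rounds to the stated 0.017. It reproduces. The documents give no sample-size or power calculation for rCBF, so there is none to check.

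**The statements side by side.**

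| Place | Stimulation target | FPN |
|---|---|---|
| 2.0, outcome list | primary | secondary |
| 8.0, rCBF headings (Aims 1 and 2) | primary | – |
| 8.0, Aim 1 rCBF analysis paragraph | secondary | ROI test at 0.017 |
| 8.0, H1.3 | primary | secondary |
| 8.0, H2.3 | primary | secondary |

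The analysis paragraph does not use the word primary for the FPN test. That status is inferred from its position under the primary heading, its alpha, and the secondary label on the sphere.

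**Sphere volumes**, V = (4/3)πr³. All sizes are from section 8.0.

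- ALFF analysis, 10 mm diameter: r = 0.5 cm, V = 0.524 cm³
- Connectivity seed and global brain connectivity, 6 mm radius: r = 0.6 cm, V = 0.905 cm³
- rCBF, 6 cm radius: r = 6 cm, V = 904.8 cm³

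The ratios are (6/0.6)³ = 1,000 and (6/0.5)³ = 1,728.

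**Dilution if the 6 cm sphere were used as written.** Assume a uniform effect and no change elsewhere. The share of the effect left in the average is effect volume divided by averaged volume. Effect sizes and brain fractions are assumptions, not figures from the documents.

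- Effect confined to 0.905 cm³, whole sphere averaged: 0.905/904.8 = 0.10%
- Same effect, half the sphere is brain: 0.905/452.4 = 0.20%
- Effect of 2 cm radius (33.5 cm³), half the sphere is brain: 33.5/452.4 = 7.4%

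**Error rate if either region could be claimed as primary.** Take two two-sided tests, each at 0.05/3, with bivariate normal statistics of assumed correlation ρ. With ρ = 0 this is 1 − (1 − 0.01667)² = 0.0331. The simulation column is from paired t-tests at n = 40, one million trials per ρ.

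| ρ | P(at least one significant), normal | Simulated |
|---|---|---|
| 0 | 0.0331 | 0.0329 |
| 0.5 | 0.0313 | 0.0315 |
| 0.7 | 0.0291 | 0.0291 |
| 0.9 | 0.0245 | 0.0248 |

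The intended rate for this outcome is 0.0167. Across one aim, three tests at 0.017 sum to 0.051. Four would sum to 0.068, or 1 − (1 − 0.017)⁴ = 0.066 if independent.

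**The case against.** The best reply is that the documents largely settle the hierarchy themselves. The target is primary in the outcome list, both headings, H1.3 and H2.3, and the opening of section 8.0 says the outcome measures stand as described. The alpha can be recovered from the 0.05/3 rule, and H1.3 itself calls for a two-tailed t-test. The figure 0.017 does not mark primary status either: the same paragraph attaches it to the whole-brain search, and the exploratory ALFF analysis uses it too. A 12 cm sphere would span more than half of the 22 cm ASL field of view, so nobody is likely to run it, and the dilution percentages describe an improbable analysis. The study is exploratory, and even the worst case moves the per-aim error rate only from about 5% to about 6.6%.

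Much of this stands. The target is the better-supported reading, the 6 cm figure is probably a unit slip, and the error inflation is both modest and conditional. But the weight of the other statements does not delete the contrary paragraph. Correcting the unit would still leave the target sphere labelled secondary. Nor is the intended size recoverable. A 6 mm radius matches the connectivity seed, while the ALFF analysis, offered as a supplement to the perfusion measure, uses a 10 mm diameter. Those differ in volume by 0.905/0.524 = 1.7 times, and neither is assigned to rCBF.

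**Conclusion.** The concern holds, and the paragraph must be corrected before analysis. The contradiction and the unusable radius are read directly from the text and need no assumption. The main harm is that one of three primary MRI outcomes, in both Aim 1 and Aim 2, lacks a single region of known size.

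The numerical consequences are conditional. The false-positive rate for the outcome rises from 1.67% to between 2.4% and 3.3% only if either region may be claimed as primary, under assumed correlations of 0.9 to 0. The loss of all but 0.1% to about 7% of a focal effect applies only if the 6 cm sphere is used literally, under the assumed effect sizes and brain fractions.

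**What to change.** Rewrite the rCBF analysis paragraph in section 8.0, before analysis, along these lines:

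- **Primary:** mean rCBF in a sphere of [x] mm radius at the stimulation target, native space, two-sided paired t-test between sessions, alpha 0.05/3.
- **Secondary:** mean rCBF in the n-back FPN mask; whole-brain voxelwise search with topological FDR.

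State the radius in millimetres. A 6 mm radius would match the connectivity seed, but the ALFF sphere is a competing precedent, so the investigators should confirm the value. Say explicitly that the same sphere and hierarchy apply to H2.3. The Aim 1 prediction in section 2.0 about FPN perfusion can stay, with a note that FPN perfusion is the secondary outcome.

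The cost is wording in the analysis plan and one confirmation from the investigators. No new data, visits or participants are needed.
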